6.1. Participant identification

We will recruit patients from the University of Wisconsin Endocrine Surgery and Otolaryngology Clinics. We will also promote the study to endocrinologists throughout the state, specifically targeting endocrinologists in areas with a greater proportion of underrepresented minorities than found in the Madison area. We have well established referral patterns from Winnebago County, IL, which has a significantly higher proportion of underrepresented minority patients than Dane County where our institution is based.

We will work closely with referring endocrinologists to perform the needed long-term follow up for the participants in the study. We will try to condense all study visits to 4 time points, which are already established for routine clinical follow up. Because participation in the study will require additional time at these appointments we will provide a small monetary reimbursement for participation in each of the study visits (\$20). The cost of all study procedures that are not the standard of care will be covered as part of participation in the clinical trial.

6.2. Screening

A member of the study staff will assess patient eligibility using the Prepatory to Research provision, as approved by the institutional review board (IRB). All protected health information used during the screening process of a potential participant will be the minimum necessary for the conduct of this study. Any protected information recorded will be destroyed at the end of the screening process. The clinical care team of the potential participant will be aware of the potential participation in this study as they will be the ones who refer the participant.

After consent is obtained, if any pre-operative procedures were not captured in the medical record, these will be conducted as necessary per standard of care prior to surgery. The study team will record the necessary data from these standard of care procedures.

A participant is enrolled prior to surgery and will undergo baseline testing of voice and swallow⁵ function and QOL assessment. They will be randomized during surgery after confirmation that there is no evidence of nodal involvement.

6.3. Recruitment and consent

The human subjects participating in this study will be recruited from the University of Wisconsin Endocrine Surgery and Otolaryngology Clinics as well as patients referred to the clinic by regional endocrinologists. A participant's decision whether or not to participate will not affect the care he or she receives as a patient. Participants will be treated according to the standard of care for their disease until

consent for the study is obtained. Participants must meet inclusion and exclusion criteria as listed above. Participants will be selected without consideration of socio-economic background or insurance status.

Following explanation of the consent form, each potential participant will be given an opportunity to read it thoroughly. Before being allowed to sign the consent form, potential participants also will be given an opportunity to ask questions. The investigator will emphasize the fact that the participant can terminate involvement at any time without any consequences. Once the consent form has been signed, the study pre-operative procedures will be performed if not already captured in the medical record.

7. Activities and measurements

Enrollment: Participants will be enrolled after signing the informed consent form.

Pre-operative visit: The pre-operative visit will include a study-required baseline assessment of every participant's voice and swallow⁵ function and a QOL survey. A baseline assessment of vocal function will be considered clinically indicated in those patients with existing voice complaints or prior neck surgery. If patients are found to have some abnormality on their vocal evaluation that would warrant intervention, they will not proceed to randomization. These pre-operative study evaluations will be coordinated with the standard collection of the participant's pre-operative medical history, physical exam, and laboratory evaluation.

Day of surgery: Once the surgeon visually confirms there is no evidence of nodal involvement intraoperatively, the participant will be randomized. Study arm randomization will be computer generated by [name] of the UW Department of Surgery Biostatistics Office and communicated to the surgeon via sealed envelope. Participants will be blinded to their treatment arm until the Day 12 visit.

Post-operative care in hospital: After surgery, participants will remain in the hospital overnight per surgeon preference and laboratory evaluations will be performed per standard of care.

Post-operative Day 1: The participant will be educated on the signs and symptoms of hypocalcemia and be given detailed instruction on how to treat these symptoms per standard of care. They will be given a study log to fill out which will allow them to record the frequency and severity of symptoms and the number of doses of calcium taken. This will be completed and returned to study staff at the Day 12 visit.

Day 12 visit: Physical and laboratory evaluations will be performed per standard of care. A comprehensive voice and swallow⁵ evaluation will be conducted; this will be considered a research procedure unless the participant is experiencing difficulty swallowing or there is evidence of vocal fold dysfunction. The participant will also complete a QOL survey and participate in a qualitative interview per study protocol.

Week 6 visit: 48 hours prior to the Week 6 visit day, participants will have a blood sample drawn to establish post-operative thyroglobulin levels and assess response to treatment. During the visit, participants will complete QoL surveys and participate in a qualitative interview. If the patient's voice or swallow function was impaired at the Day 12 visit, additional voice and swallow⁵ evaluations will also be performed.

At this time the treating endocrinologist will assess the subject's risk profile based on the criteria outlined in section 3 of the protocol. If the patient is classified as intermediate- or high-risk or if the patient is classified as low-risk but chooses to undergo RAI remnant ablation, he or she will be treated according to the following standard schedule:

- Day 1: rTSH injection
- Day 2: rTSH injection
- Day 3: 50 mCu I-131 therapy administered²
- Day 5: Stimulated thyroglobulin lab
- Day 5-17: Whole Body Scan performed

Month 6 visit: Physical and laboratory evaluations, as well as an ultrasound of the neck, will be performed per standard of care. PTH and calcium samples required for the study will be drawn at this time. A QOL survey and qualitative interview will be completed. If the patients' voice or swallow function was impaired at the Week 6 visit, additional voice and swallow⁵ evaluations will also be performed.

1 Year visit: Patients will receive a neck ultrasound and labs per standard of care. If a patient underwent RAI remnant ablation, a stimulated thyroglobulin level after rTSH administration will be obtained to assess response to therapy. A QOL survey and qualitative interview will be completed. If the patients' voice or swallow⁵ function was impaired at the Month 6 visit, additional voice and swallow evaluations will also be performed.

Follow-up: Patients will receive a quality improvement follow-up survey between 1 and 6 weeks after the completion of their last study activity. Patients who meet criteria for long term follow-up will continue to be followed through chart review and the endocrine surgery outcomes database.

Time required for study procedures: 120 minutes for voice and swallow evaluation^{3,5}
15-30 minutes for QOL survey
60-90 minutes for qualitative interview

7.1. Table: Time points for data collection

Variable	Unit	Time Points for Data Collection					
		Pre	Post-Op Day 1	Post-Op 2 Weeks	Post-Op 6 Weeks	Post-Op 6 Mo	Post-Op 12 Mo
Phonation Threshold Pressure	mmHg or cmH2O	X		X	Performed only if prior exam is abnormal		
Dysphonia Symptom Index	Score	X		X	Performed only if prior exam is abnormal		
CAPE-V Global Dysphonia	Rating	X		X	Performed only if prior exam is abnormal		
CAPE-V Rough	Rating	X		X	Performed only if prior exam is abnormal		
CAPE-V Breathy	Rating	X		X	Performed only if prior exam is abnormal		
CAPE-V Strain	Rating	X		X	Performed only if prior exam is abnormal		

² Since no patient will have significant nodal involvement, low-dose ablation should be appropriate for all patients. No RAI will be required for participants determined to be low-risk.

³ If voice and swallow are normal at any post-op visit, then evaluations will not be performed at subsequent follow up time points

Variable	Unit	Time Points for Data Collection					
		Pre	Post-Op Day 1	Post-Op 2 Weeks	Post-Op 6 Weeks	Post-Op 6 Mo	Post-Op 12 Mo
CAPE-V Pitch	Rating	X		X	Performed only if prior exam is abnormal		
CAPE-V Loudness	Rating	X		X	Performed only if prior exam is abnormal		
CAPE-V Other	Rating	X		X	Performed only if prior exam is abnormal		
GRBAS Grade	Rating	X		X	Performed only if prior exam is abnormal		
GRBAS Rough	Rating	X		X	Performed only if prior exam is abnormal		
GRBAS Breathy	Rating	X		X	Performed only if prior exam is abnormal		
GRBAS Asthenia	Rating	X		X	Performed only if prior exam is abnormal		
GRBAS Strain	Rating	X		X	Performed only if prior exam is abnormal		
Stroboscopy Edge Left & Right	Rating	X		X	Performed only if prior exam is abnormal		
Stroboscopy Phase Symmetry	Rating	X		X	Performed only if prior exam is abnormal		
Stroboscopy Amplitude, L & R	Rating	X		X	Performed only if prior exam is abnormal		
Stroboscopy Vibratory	Rating	X		X	Performed only if prior exam is abnormal		
Glottal Function Index	Rating	X		X	Performed only if prior exam is abnormal		
Penetration Aspiration Scale ¹	Rating	X		X	Performed only if prior exam is abnormal		
SF-12 MCS	Score	X		X	X	X	X
SF-12 PCS	Score	X		X	X	X	X
EAT-10	Score	X		X	X	X	X
EORTC QLQ-30	Score	X		X	X	X	X
THYCA-QoL	Score	X		X	X	X	X
Voice Handicap Index Total	Score	X		X	X	X	X
Voice Handicap Index Function	Score	X		X	X	X	X
Voice Handicap Index Emotion	Score	X		X	X	X	X
Voice Handicap Index Physical	Score	X		X	X	X	X
Interview	Codes, Themes	X		X	X	X	X
Calcium	Lab	X	X	X		X	Performed only if month 6 value is abnormal
PTH	Lab	X	X	X		X	Performed only if month 6 value is abnormal

Variable	Unit	Pre	Time Points for Data Collection				
			Post-Op Day 1	Post-Op 2 Weeks	Post-Op 6 Weeks	Post-Op 6 Mo	Post-Op 12 Mo
Vitamin D (if PTH is high)	Lab	X					
Neck ultrasound	Imaging	X				X	X
FNA result	Lab	X					
Hypocalcemia symptom log	Rating			X			
TSH & repeat TSH (if needed)	Lab				X	X	X
Radioactive Iodine scan dose and scan results (randomized patients only)	Imaging				X ⁴		If indicated clinically
Unstimulated Tg level	Lab				X	X	X
Stimulated Tg level	Lab				X ⁵		X ⁵

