1.2. Rationale and hypothesis

We propose a clinical trial in which 70 - 140 patients undergoing surgery for PTC with no pre-operative evidence of distant metastasis will be enrolled into one of three treatment arms: total thyroidectomy with prophylactic central neck dissection, total thyroidectomy without central neck dissection or standard of care. The total thyroidectomy patients will be randomized into one of the first two arms. The standard of care patients, patients who are not eligible for the randomization arms pre-operatively or are unable to be randomized intraoperatively, will be enrolled into the third study arm and will not have any aspect of their cancer care modified by study participation but will otherwise follow the same follow up study assessment schedule as the patients in the randomization arms. In the absence of this clinical trial, patients seen at our center would be offered a total thyroidectomy without central neck dissection, which is our current practice standard. At many other major academic centers, however, a prophylactic central neck dissection is the standard of care. Currently about 50% of high volume institutions are doing a central neck dissection routinely in their practice. While performing a central neck dissection may increase the risks of surgery it may also decrease the risk of recurrence. We do not know, given the presently available data, which will be greater, and therefore this study has true clinical equipoise.

Our hypothesis is that total thyroidectomy with prophylactic central neck dissection will result in a higher complication rate in comparison with total thyroidectomy alone for papillary thyroid cancer.

2. Objectives

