Eligible patients will have a thyroid nodule >1 cm in size that is consistent with or suspicious for PTC on a pre-operative biopsy. All biopsies will be reviewed by pathology to confirm eligibility. Patients with T4 (tumor of any size that extends beyond the thyroid) tumors, history of degenerative neurological diseases, pre-operative vocal cord paralysis or other vocal cord pathology will be excluded. All patients will undergo a comprehensive neck ultrasound to evaluate for lymphadenopathy by an experienced thyroid radiologist. A comprehensive evaluation of lymph nodes in levels 1-6 will be performed. If the patient is proven to have lymph node involvement they will be ineligible for the randomization arms.

Patients without evidence of nodal involvement on pre-operative imaging will be eligible for the randomization arms of the trial and consented pre-operatively. Per standard of care at our institution and the recommendations of the ATA, thyroid cancer patients are offered various surgical treatments depending on the nature of their disease. For example, for those whose cancer is limited to only one side of the thyroid, a partial lobectomy may be the appropriate treatment. For this reason, we will only approach patients who have elected to undergo total thyroidectomy for the randomization arms. Patients who are eligible for the trial but not for randomization (i.e. have evidence of lymph node disease or are choosing a thyroid lobectomy) will be approached for consent into the standard of care arm.

Pre-Operative Screening and Testing: Pre-operative laboratory testing will include calcium, PTH, and Vitamin D testing (Aim 1), a comprehensive voice and swallow¹ evaluation (Aim 2), and a complete quality of life evaluation using validated questionnaires and semi-structured interviews (Aim 3). Patients eligible for the randomization arms will then be randomly assigned - after intraoperative confirmation of no suspicious adenopathy or gross local invasion - to one of two treatments on the day of surgery; Arm 1: total thyroidectomy alone, or Arm 2: total thyroidectomy with ipsilateral prophylactic CND. Randomization will be stratified by both age and tumor size to allow appropriate comparisons between groups. Allocation schedule will not be known to study staff prior to consenting.

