Post-operative follow-up: Post-operative follow-up will be done in the hospital on post-operative Day 1, and clinic follow up will occur at Day 12, Week 6, Month 6, and 1 Year. Patients will be discharged with thyroid hormone that will be administered at 1.5-1.7 mcg/kg daily. Patients will be provided a hypocalcemia symptom log and will be requested to record their calcium intake and symptoms daily. When they have symptoms they will be asked to record the time of the symptoms, what the symptoms were, the severity of the symptoms (scale of 1-5), the amount of calcium taken to treat the symptoms, and the time to symptom resolution.

All patients will be seen in follow up in the clinic in approximately 2 weeks. A calcium and PTH level will be obtained at that visit. Patients will be asked about their calcium intake and their symptoms of hypocalcemia, and their symptom log will be reviewed by study staff (Aim 1). Their symptom log will be collected at the two-week appointment and abstracted by study staff to determine the total volume of calcium supplementation consumed, the type and frequency of hypocalcemia symptoms, and the severity of those symptoms when they occurred.

Comprehensive voice and swallow⁵ evaluations will also be performed at the Day 12 visit, and these evaluations will be repeated at Week 6, Month 6, and 1 Year visits (Aim 2) if abnormalities or complaints were noted at the previous time point. All of the voice assessments listed in section 2.2 are part of a standard voice evaluation which is done routinely for patients with a history of previous neck surgery or any voice concerns, either pre-operatively or post-operatively. The video swallow exam is normally only done if there are concerns with voice or swallow function post-operatively. If deficits are observed at Day 12, appropriate treatment will be provided. This may include watchful waiting, behavioral therapy, diet modification, use of injectables, or further surgery. Follow-up assessments at Week 6, Month 6, and 1 Year will, in these cases, provide preliminary data on treatment outcomes. Patients will also complete QOL surveys and interviews to determine the effects (if any) of post-operative complications on overall well-being at each visit (Aim 3).

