In all intermediate- and high-risk subjects and low-risk subjects who choose to undergo RAI remnant ablation therapy, radioactive iodine will be administered at 4-20 weeks post-operatively and will be administered with rTSH. For consistency all subjects will be treated with 50 mCi of radioactive iodine unless it is strongly recommended otherwise based on specific features of the individual patient. Microscopic nodal involvement found on pathologic review will not influence the treatment dose of radioactive iodine, but the presence or absence of micrometastatic versus macrometastatic disease will be tracked for future analyses. Thyroglobulin levels will be checked after the rTSH stimulation in order to assess the burden of disease prior to radioactive iodine treatment. Following radioactive iodine administration, levothyroxine will be administered to maintain TSH < 0.5 uIU/mL. Labs will be checked at 6-8 week intervals until TSH level is in the goal range and stable.

At Month 6 and 1 Year visits, TSH, unstimulated thyroglobulin and anti-thyroglobulin antibody will be measured. Additionally, all patients will receive a neck ultrasound at these time points to further evaluate for recurrence.

If the subject underwent RAI remnant ablation, recombinant TSH will be administered and a blood sample testing for the stimulated thyroglobulin level will be obtained at the 1 Year visit. If the stimulated thyroglobulin is greater than 2 ng/mL and the neck ultrasound is negative, a whole body scan will be obtained. Elevated thyroglobulin and/or positive whole body scanning will prompt further evaluation with ultrasound, CT, MRI, or CT-PET as needed. All participants will be followed for a minimum of 1 year after treatment. Long term follow-up tracking the incidence of disease recurrence will be conducted throughout the entirety of the study, with the goal of tracking patients beyond the active study phase through our prospective endocrine surgical database.

Long-term follow-up: Participants who receive a diagnosis of PTC, as confirmed by final surgical pathology, and continue to receive care within the University of Wisconsin Hospital system will be followed through chart review and the endocrine surgery outcomes database until their cancers recur or they are lost to follow up. Clinical documentation of cancer recurrence only, if it occurs, will be abstracted from their electronic medical records.

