Potential risks of the VF swallow study include gagging, choking, and fainting. There is minimal discomfort and minimal risk associated with the endoscopy procedures used during the evaluations. The rigid endoscope is simply inserted into the mouth, without the need for any topical anesthesia. It is possible that the participant may feel a slight amount of anxiety due to having something placed into his/her mouth, although in our experience this is very rare. There may be discomfort with the face mask or feelings of unease or anxiety during the airflow recordings due to the facemask or the tube in the participant's mouth. The likelihood of these risks occurring is small and further reduced by providing the participants adequate time to rest between tasks. Medical staff will be immediately on hand in our hospital setting if these events should occur.

Risks associated with psychological stress

Participants will be discussing their experiences and any adverse outcomes they have experienced in the post-operative period. This may cause changes in thought processes and emotion. These changes will mostly be transitory; however they may be recurrent, or even permanent.

Risks associated with loss of confidentiality

There is a risk that information recorded about participants will be shared with people who would not normally have access to this information.

Risk of radioactive iodine standardization

There is a risk that health care providers following standard of care procedures would treat a study-eligible patient with higher doses of radioactive iodine (usually 100 mCi) than is allowed under this protocol. This theoretical under treatment could possibly contribute to a recurrence or persistence of the original disease, requiring either additional surgery or radioactive iodine treatment(s) in the future. If there are concerns about the dosing of radioactive iodine the case will be presented at our multidisciplinary tumor board and a joint decision made by all providers whether it is appropriate for the patient to remain on the protocol or not and this will be communicated to the patient so they can decide how they would like to proceed.

Unknown risks

This study may involve risks to the participant which are currently unforeseeable. We will inform participants as soon as possible if we discover any information that may affect the participant's health, welfare, or decision to be in this study.

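### The 50 mCi radioactive iodine default is not limited by arm, and its stated premise of no significant nodal disease is false for the standard of care arm

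*Combined protocol and SAP*

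**What the plan says.** **The RAI rule.** Section 3 (Post-operative follow-up) gives RAI as follows: "In all intermediate- and high-risk subjects and low-risk subjects who choose to undergo RAI remnant ablation therapy". It then sets the activity: "For consistency all subjects will be treated with 50 mCi of radioactive iodine unless it is strongly recommended otherwise". The exception rests on features particular to a given patient. Section 7 (Week 6 visit) repeats 50 mCi as the standard schedule once the endocrinologist has assigned a risk class. Footnote 2, attached to that step and printed with the section 7.1 table, gives the reason: "Since no patient will have significant nodal involvement, low-dose ablation should be appropriate for all patients". Its second sentence adds that low-risk participants need not have RAI. None of these places names an arm.

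**Who is in the study.** Section 3 (Participant Identification and Eligibility) describes the candidates for the standard of care arm: "Patients who are eligible for the trial but not for randomization (i.e. have evidence of lymph node disease or are choosing a thyroid lobectomy"). Section 3 (Operative Procedure) moves patients who fail screening during surgery into the same arm, and nodal metastasis found at operation is one reason for failing. The node-negative inclusion criterion (section 4.1, item 2) and the intra-operative nodal exclusion (section 4.3, item 1) are marked as applying to the randomization arms only.

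**How that arm is treated.** Section 1.2 says that these patients "will not have any aspect of their cancer care modified by study participation". The opening of section 5 says that they have no specific treatment intervention, and section 5.3 leaves treatment to patient and physician.

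**The acknowledged risk.** Section 9.1 notes that usual practice may involve "higher doses of radioactive iodine (usually 100 mCi) than is allowed under this protocol", and that the resulting theoretical under-treatment could contribute to recurrence or persistence. Concerns about dosing go to the tumor board, which decides whether the patient stays on protocol.

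**The concern.** The post-operative rule reads as if every participant were clinically node-negative. That fits the two randomized arms as far as clinically evident disease goes. It does not fit an arm that takes in patients because they have nodal disease.

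Two things are at stake. The first is safety: the only justification given for a treatment default fails for a group that the protocol admits, and the protocol itself names possible under-treatment as a risk of that default. The second is what the standard of care data mean. The Summary says that the three cohorts will be compared, including on recurrence. If the default is applied to the third cohort, its recurrence and thyroglobulin results come partly from a protocol-driven treatment, although the cohort is described as unmodified care.

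**Working it through.** The point is about consistency of text, so the check is a cross-reading, followed by the one piece of arithmetic that bears on scale.

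**Step 1. Does the rule reach the standard of care arm as written?**
- Section 3 and the Week 6 text in section 7 define their scope by risk class and receipt of RAI, not by arm.
- Section 1.2 puts standard of care patients on the same follow-up assessment schedule as the randomized patients, and section 7 sets out the RAI steps within that schedule.
- Section 9.1 describes the dose restriction as applying to patients eligible for the study. Section 3 uses the same idea for standard of care candidates: eligible for the trial, though not for randomization.
- Elsewhere the protocol restricts scope explicitly when it means to: Schedule of activities notes 4 and 17, sections 4.1 (item 2), 4.3 and 7.2, and the RAI row of the section 7.1 table. There is no such restriction on the RAI treatment rule.

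So, read literally, the rule does reach that arm.

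**Step 2. Is the premise true there?**

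| Statement | Randomized arms | Standard of care arm |
|---|---|---|
| Node-negative on pre-operative ultrasound required | Yes (4.1) | No |
| Nodal disease at surgery excludes | Yes (4.3) | No; the patient continues in this arm (3) |
| Footnote 2 premise | Holds for clinically evident disease | False for patients entered because of nodal disease |
| Care set by protocol | Yes | No (1.2, 5, 5.3) |
| 50 mCi default if RAI is given | Yes | Yes, as written (3, 7) |

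The last two rows conflict for the standard of care arm.

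**Step 3. Do the exceptions resolve it?** Section 3 allows departure for an individual when it is strongly recommended. Section 9.1 sends concerns to the tumor board. Section 5.3 asks only for a preference. A physician who prefers another activity, without a strong recommendation for it, meets section 5.3 but not section 3. The exceptions therefore narrow the conflict without closing it, and they do nothing about the premise.

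**Step 4. Scale, from section 8.1.**
- Cancer pool: 350 × 0.30 = 105 a year, as stated.
- Ultrasound-negative: 105 × 0.85 = 89.25, matching the stated figure of about 89.
- Ultrasound-positive: 105 × 0.15 = 15.75, about 16 a year.

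These 16 cannot be randomized and could be approached for the standard of care arm if otherwise eligible. How many would qualify on age, T4 and metastasis criteria, consent, and receive RAI is not in the documents. Nor is the number whose nodal disease is found only at surgery.

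**The case against.** The best defense is that the text was evidently written for the randomized arms. The RAI dose and scan row in the section 7.1 table is restricted to randomized patients, as is the thyroglobulin-triggered scan in Schedule of activities note 4. After setting the activity, section 3 discusses only microscopic nodal involvement found on pathology, which is the clinically node-negative case. Three arm-specific statements (sections 1.2, 5 and 5.3) would naturally be read as overriding general wording. This is a fair account of probable intent. But the two restrictions cover data collection and one scan, not treatment, and the protocol gives no order of precedence.

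The defense is right against several stronger readings that a reader might infer:

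- **That a site cannot comply with both sets of statements.** The documents do not support this. Proven nodal disease can be a feature that leads to a strong recommendation to depart from the default, so a clinician can often satisfy both.
- **That 16 patients a year is the number affected, or that 100 against 50 mCi measures under-treatment in them.** The 16 is a clinic pool before eligibility, consent and RAI use. The 100 mCi figure in section 9.1 concerns study-eligible patients in general and is not specific to node-positive patients.
- **That the discharge thyroid hormone rule has the same fault** ("Patients will be discharged with thyroid hormone that will be administered at 1.5-1.7 mcg/kg daily"). Nothing says that standard of care patients would otherwise receive something different, and section 9.1 lists suppressive hormone replacement among standard care items.
- **That patients whose cancer is not confirmed are caught.** The Week 6 schedule follows assignment of a cancer risk class, and these patients have no evident route into it.
- **That the trial's main comparison is damaged.** Section 8.2 analyzes CND against no CND only, and the section 8.1 power calculation concerns those two arms.

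**Conclusion.** The concern stands in a limited form. The RAI default and its justification are not restricted by arm. The justification is false for standard of care patients entered because of nodal disease, and the default conflicts with three statements that this arm's care is not set by the protocol. The individual exception and the tumor board route reduce the practical effect but leave both the default and the false premise in place.

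The effect is confined to standard of care patients who receive RAI, and to the interpretation of that cohort, which has no place in the section 8.2 model. Because the RAI row of the section 7.1 table is restricted to randomized patients, that table would not show which rule had been followed in the cohort. The number of patients involved cannot be derived from the documents.

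The conclusion assumes only that the text means what it says about scope. If the sponsor intended the rule for Arms 1 and 2 alone, the defect is one of wording, but it is safety-relevant wording and should be corrected. No view is taken on which activity or clinical rule is right.

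**What to change.** Reconcile section 3 (Post-operative follow-up), section 7 (Week 6 visit), footnote 2 and section 9.1 with sections 1.2, 5 and 5.3 and with the eligibility and operative text in section 3:

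1. State, wherever the RAI rule appears, which arms it covers.
2. Limit the premise in footnote 2 to the arms for which it holds.
3. Say in section 9.1 which participants are exposed to the dose-standardization risk and to the tumor board route.

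The sponsor's clinicians decide which rule applies to the standard of care arm; the statistical requirement is only that the protocol gives one answer.

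The cost is wording in about four places, with consent text checked to match. No procedures, visits or patients are added, and the sample size and the randomized analysis do not change.
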